#### **12.5.2 Rapid Diagnostics**

For unscheduled visits and clinical diagnostics, rapid diagnostic tests may be utilized for determination of an acute malarial illness; however, they cannot be used in place of microscopy for determination of parasitemia status.

#### **12.5.3 Malaria Polymerase Chain Reaction**

While detection of parasites on thick BS remains the most common primary endpoint in human challenge trials, both PCR- and nucleic acid sequence-based amplification methods have been increasingly used to support BS data in malaria vaccine trials. These research molecular assays have significantly increased sensitivity for detection of *P. falciparum* blood-stage infection approaching 20 parasites/mL, often resulting in diagnosis 2-4 days earlier than by paired thick BS. Quantification of parasite density by these methods allows evaluation of parasite growth curves for assessing the utility of partially-effective vaccine candidates. LMIV has also developed a research quantitative PCR (qPCR) that detects 18s of *P. falciparum* with a detection limit of at least 20 parasites/mL; this technique will be used during the study for comparison to traditional thick BS.

*P. falciparum* qPCR may be performed from all scheduled visits with a malaria BS noted (see [Appendix A](#)) to capture infections that remain below the detection limit for microscopy. For subject convenience, a finger-prick sample can be used for both preparation of the microscopy

slide and for deoxyribonucleic acid (DNA) preservation, but venous blood draws can also be used.

## 12.6 Immunologic Laboratory Testing

### 12.6.1 ELISA

Anti-Pfs230 ELISAs will be performed on sera obtained from immunized subjects at MRTC in Bamako, Mali and may also be performed at collaborating laboratories.

For Pfs230D1M ELISAs, microwell plates are first coated with antigen solution. Plates are washed with TRIS-buffered saline (TBS) containing Tween-20 (T-TBS) and blocked with TBS containing skim milk powder. After washing with T-TBS, diluted serum samples are added in triplicate and incubated at room temperature for 2 hours. After incubation, unbound antibodies are removed by washing the plates with T-TBS, and alkaline phosphatase-conjugated goat anti-human IgG solution is added to each well and incubated for 2 hours at room temperature. Plates are then washed with T-TBS, followed by adding phosphatase substrate solution to each well; the plates are then covered and incubated for 20 minutes at room temperature for color development. The plates are read immediately at 405 nm with a microplate reader. The optical density values are used to determine antibody levels by comparing to a standard curve generated from a known positive-control plasma included on each ELISA plate.

Additionally, the magnitude and kinetics of IgG responses may be explored over time post-vaccination. Quality of antibody responses may be explored via antibody avidity as well as assessment of antibody subclasses to provide useful insight into the humoral immune response.

### 12.6.2 Transmission Assays

The transmission-blocking assay which will be conducted is summarized in [Table 14](#).

**Table 14. Transmission-Blocking Assay**

Assay	Mosquitoes	Test Samples	Site
Standard Membrane-Feeding Assay	Lab strain ( Anopheles stephensi )	Membrane feeds with lab cultured parasites mixed with test serum/plasma	LMIV LMVR
Direct Skin Feeding Assay	Colony strain ( Anopheles coluzzi )	Mosquitoes feed directly on skin of study participants	MRTC

Feeding assays demonstrate biologic activity of transmission-blocking antibodies and are critical to selection of TBV candidates. Subjects will be screened periodically by BS (as seen in [Appendix A](#)) for the presence of asexual parasites and gametocytes.

### 12.6.3 Standard Membrane Feeding Assays

Membrane-feeding assays demonstrate biologic activity of transmission-blocking antibody and are critical to selection of vaccine candidates. SMFAs will be performed on sera obtained at baseline and periodically after vaccination as outlined in [Appendix A](#). In a SMFA, test serum obtained from immunized subjects is mixed with parasites from a laboratory culture and the mixture is placed in a feeding cup covered with an artificial membrane. Pre-starved mosquitoes from a laboratory colony are allowed to feed through the membrane. A similar procedure is carried out on a malaria-naïve control serum at the same time using mosquitoes raised from the same laboratory colony. One week after the feed, mosquitoes are dissected, and midguts are stained with mercurochrome for the oocyst form of the parasite. The reduction of the proportion of oocyst-laden mosquitoes or the reduction of average oocyst numbers per mosquito compared to mosquitoes fed on the control group demonstrate biologic function of the antibody, and may be predictive of efficacy in the field. SMFA results have been shown to correlate with ELISA antibody titers against Pfs25 in several species. The SMFAs will be conducted at LMIV and Laboratory of Malaria and Vector Research (LMVR) in Rockville, Maryland.

SMFA will be conducted at LMIV using laboratory-strain mosquitoes and parasites. Assays will compare feedings with the following:

- Plasma/sera.
- IgGs purified from the selected plasma/sera, mixed with a malaria-naïve human sera pool (to eliminate non-specific factors which may be present in plasma).

To confirm anti-Pfs230-specific TBAs, SMFAs may also be conducted by the following methods:

- Using Pfs230-specific IgG purified using affinity chromatography.
- Using test plasma/sera that has been depleted of Pfs230-specific antibodies using recombinant Pfs230 proteins.

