#### 8.1.2 Secondary Endpoints

- *P. falciparum* asexual parasitemia as measured by blood smears after receipt of 3rd and 4th vaccination and analyzed with the main group
- Anti-Pfs230D1M immunoglobulin (Ig) G levels as measured by ELISA
- Transmission-reducing activity (TRA)/Transmission-blocking activity (TBA) of induced antibody in SMFA

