### 8.2.2 Secondary Endpoints

- *P. falciparum* asexual parasitemia as measured by blood smears (All Arms except Arms 3e/3f)
- Incidence of local and systemic AEs and SAEs (All Arms except Arms 4a/4b)
- Anti-Pfs230D1M immunoglobulin (Ig) G levels as measured by ELISA (All Arms except Arms 4a/4b)
- Transmission-reducing activity (TRA)/Transmission-blocking activity (TBA) of induced antibody in SMFA (All Arms except Arms 4a/4b)

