#### **17.1.2 Secondary Objective**

The secondary objectives of this study are:

- To assess ELISA titer response to Pfs230D1M-EPA/AS01 in Malian children (Arms 1a, 2a)
- To assess functional antibody response by SMFA to Pfs230D1M-EPA/AS01 in Malian children (Arms 1a, 2a)

Anti-Pfs230 antibody will be measured by ELISA on vaccination days, 2 weeks after each vaccination, and periodically until study completion. Antibody responses over time will be shown graphically with geometric mean antibodies and the associated confidence intervals based on the t-distribution applied to the log-transformed responses. We will compare antibody and functional assay responses within arms over time. We will also look at differences in antibody decline over time in the vaccination groups. Graphs will display transmission-blocking assays as a function of ELISA antibody levels.

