### 17.3.1.3 SMFA Analysis

For a group of 15 participants we anticipate at least 60% power to detect a difference in TRAs of 32% (the observed difference in #17-I-N006) and 80% power for a 40% difference. These Power calculations come from a simulation assuming values similar to the SMFA data from Protocol #17-I-N006, where the control group had an average TRA of 38 (sd 39) and a treatment group with sd 34. Thus counting the number of significant comparisons out of a thousand comparisons between random normal draws from  $N(38,39)$  and  $N(38+40, 34)$  using the Wilcoxon test can give approximate power.

If TBAs are used, we will standardize the TBAs to a common target control mean first using the methods of Swihart, Fay, & Miura (2018). A nice feature of the standardized TBA is that its power is identical to those of the TRA.

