### 17.3.2.3 Analysis

The primary DSF analysis will use a GEE model with compound level clustering and the number of positive DSFs as outcome will be used for analysis with an offset for the number DSF tests. The primary parasitemia analysis will be analogous. The primary analysis population will follow the intention-to-treat principle. Additional analyses will explore the effects of different covariates such as time since start of the rainy season, SMC treatment, compound-level vaccine coverage, or proximity to a control compound on vaccine efficacy.

The primary safety and immunogenicity analyses will compare the rates of AEs or levels of antibody/activity between vaccinated and control individuals using standard statistical methods that respect compound-based randomization, as appropriate.

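### No between-arm SMFA analysis names the Day 0 value as a covariate, and the pilot analysis relies on within-arm change over time

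*Combined protocol and SAP*

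**What the plan says.** The secondary endpoint in Section 8.1.2 is "Transmission-reducing activity (TRA)/Transmission-blocking activity (TBA) of induced antibody in SMFA"; Section 8.2.2 repeats it for the main study.

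On measurement, Section 12.6.3 feeds mosquitoes on the participant's serum, and "A similar procedure is carried out on a malaria-naïve control serum at the same time using mosquitoes raised from the same laboratory colony". Reductions "compared to mosquitoes fed on the control group demonstrate biologic function of the antibody, and may be predictive of efficacy in the field". On timing, "SMFAs will be performed on sera obtained at baseline and periodically after vaccination". Appendix B draws Day 0 blood for ELISA and SMFA in the vaccinated arms. The Appendix A footnotes, however, make the Day 0 SMFA permissive rather than required.

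On analysis:
- Section 17.1.2 (pilot) names only the vaccine arms, 1a and 2a, in its SMFA objective and states: "We will compare antibody and functional assay responses within arms over time".
- Section 17.3.1.3 (power) compares two groups with a Wilcoxon test on one value per participant, assuming that "the control group had an average TRA of 38 (sd 39) and a treatment group with sd 34".
- Section 17.3.2.3 (main) compares "levels of antibody/activity between vaccinated and control individuals" by standard methods that respect the compound randomisation.
- Section 17.2.3 assigns ELISA and SMFA to a GEE clustered on compound.
- Section 17.2.2 limits main-phase ELISA and SMFA to a subset of samples picked on direct skin feed or blood smear results.

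None of these names the Day 0 value as a covariate in a comparison of arms.

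**The concern.** The participants live with malaria. Section 1.1 says exposed populations acquire antibody to Pfs230, and Section 3.1.2 reports that a few Malian adults already had a Pfs230 response at baseline. TRA scored against naive serum can therefore include activity that the vaccine did not produce. A control-arm mean of 38 with SD 39 is consistent with that. The participant's own Day 0 assay is the obvious way to remove stable differences between people, and the plan already provides for it.

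Two things are at stake. First, the arm comparison may give up precision where power is already low: with 15 per arm, Section 17.3.1.3 accepts about a 40% chance of missing the 32-point difference seen in adults. Second, the pilot's stated analysis uses Day 0 in its weaker role, as the start of a within-arm change. That change runs from before the transmission season into it, so natural exposure during follow-up cannot be told apart from vaccine effect.

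**Working it through.** **1. Reproducing the stated power.** Inputs from Section 17.3.1.3: control N(38, 39), vaccine N(38 + d, 34), 15 per arm, Wilcoxon test. The two-sided 0.05 level is taken from Section 17.3.1.2, since 17.3.1.3 does not restate it. With 20,000 simulated trials:
- d = 32: 0.601 (stated: at least 60%).
- d = 40: 0.785 with exact p-values, 0.790 with asymptotic ones (stated: 80%).

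A one-sided test gives 0.73 and 0.88, which does not match. Capping TRA at 100 changes little (0.603 and 0.786). The stated figures are therefore those of a two-sided, two-group test with no baseline term.

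**2. Chance imbalance at Day 0.** Assume the Day 0 SD is 39, as in controls. The standard error of the arm difference in mean Day 0 TRA is 39 × √(2/15) = 14.2 points. At a correlation of 0.5 the regression slopes are 0.5 (control) and 0.5 × 34/39 = 0.44 (vaccine). An imbalance of one standard error then moves the follow-up difference by about 6 to 7 points, against a target of 32.

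**3. Power with Day 0 used.** Let b and e be independent standard normals, and ρ the Day 0 to follow-up correlation.
- Day 0: 38 + 39b in both arms (assumed).
- Control follow-up: 38 + 39(ρb + √(1 − ρ²)e).
- Vaccine follow-up: 38 + d + 34(ρb + √(1 − ρ²)e).
- Rank ANCOVA: regress ranked follow-up on arm and ranked Day 0, t-test on 2 × 15 − 3 = 27 degrees of freedom. ANCOVA: the same, unranked.
- Change score: Wilcoxon on follow-up minus Day 0.

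Power from 4,000 simulated trials per row:

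| ρ (control / vaccine) | d | Post-only Wilcoxon | Change score | ANCOVA | Rank ANCOVA |
|---|---|---|---|---|---|
| 0 / 0 | 32 | 0.60 | 0.32 | 0.63 | 0.60 |
| 0.3 / 0.3 | 32 | 0.60 | 0.44 | 0.68 | 0.64 |
| 0.5 / 0.5 | 32 | 0.60 | 0.58 | 0.75 | 0.71 |
| 0.7 / 0.7 | 32 | 0.60 | 0.79 | 0.89 | 0.84 |
| 0.5 / 0.2 | 32 | 0.59 | 0.46 | 0.66 | 0.65 |
| 0 / 0 | 40 | 0.80 | 0.48 | 0.82 | 0.80 |
| 0.3 / 0.3 | 40 | 0.79 | 0.63 | 0.85 | 0.82 |
| 0.5 / 0.5 | 40 | 0.79 | 0.76 | 0.91 | 0.88 |
| 0.7 / 0.7 | 40 | 0.79 | 0.93 | 0.98 | 0.96 |
| 0.5 / 0.2 | 40 | 0.79 | 0.66 | 0.86 | 0.84 |

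**4. Why not a change score.** Summed over the two arms, the post-only variance is 39² + 34² = 2677. For the change it is 2677 + 2 × 39² − 2ρ(39² + 34 × 39) = 5719 − 5694ρ. The two are equal at ρ = 3042/5694 = 0.53. Below about 0.5 a change score loses power, as the table shows.

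**5. Within-arm change in the pilot.** Table 7 puts pilot enrolment in April and May 2019, with vaccination continuing to September and October. Section 9.1 gives the transmission season as June to December. After dose 3, Table 8 reports *P. falciparum* positivity in 51.9% of those aged 5-8 and 71.2% of those aged 9-18, pilot and main participants and both arms pooled. Section 1.1 suggests that natural infection may boost the vaccine response. The Day 0 to follow-up change thus spans heavy exposure, and 17.1.2 sets no concurrent control against it.

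**The case against.** A reader might infer that scoring against naive serum biases the SMFA result by crediting natural immunity to the vaccine. The documents do not support that for the arm contrast. Comparator units are randomised, come from the same exposed population and are scored against the same naive serum, so natural activity cancels on average. Section 12.6.3 describes how the assay is scored; it sets no rule for attributing activity to the vaccine. It also lists Pfs230-specific purification and depletion as optional confirmation. A Day 0 covariate would not itself establish antigen specificity.

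A reader might also turn the control mean and SD into a share of comparator sera that would count as active. The plan sets no TRA threshold for a positive result, and nothing shows that comparator sera lack Pfs230 antibody.

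Nor does the plan ignore Day 0 altogether. Section 17.1.2 uses it within arms, and Section 17.3.1.2 plans signed-rank tests of ELISA change from baseline. Section 17.3.1.3 is a power calculation, and neither 17.3.2.3 nor the GEE in 17.2.3 excludes covariates. The gap is one of specification.

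The size is uncertain too. Section 3.2.3 reports 100% TRA in adults two weeks after dose 2 and over 90% at twelve weeks, so vaccinees' later values may depend little on Day 0. With correlations of 0.5 and 0.2 the gain is only about 5 points.

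All of this stands and limits the point. It does not remove the absence of a named baseline adjustment, or the weakness of within-arm change as evidence of vaccine effect.

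**Conclusion.** The point holds as one of efficiency and specification on a secondary endpoint. Natural activity adds variance and chance imbalance at 15 per arm; it does not bias the randomised contrast on average. For a 32-point difference, Day 0 adjustment by rank ANCOVA gains nothing at zero correlation and costs essentially nothing there. It gains about 4, 11 and 24 points at correlations of 0.3, 0.5 and 0.7, and about 5 points if the correlation is 0.5 in controls and 0.2 in vaccinees.

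These gains rest on correlations that the documents do not give, on an assumed Day 0 mean of 38 and SD of 39, and on a model without clustering. No gain was computed for ELISA. In the main phase, samples are selected on outcomes that the vaccine is meant to change. Randomisation no longer guarantees balance in that subset, and Day 0 adjustment does not repair it.

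**What to change.** In Sections 17.1.2 and 17.3.2.3, make the SMFA and ELISA comparison a between-arm comparison adjusted for the participant's own Day 0 value. Use ANCOVA, rank ANCOVA or a baseline covariate in the GEE, respecting vaccine-unit clustering. Do not use a change score. Name the comparator arms in 17.1.2, and keep within-arm change over time as description.

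In 12.6.3, add that the naive-serum feed scales each assay, and that induced activity is judged from the baseline-adjusted contrast with the comparator arm.

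In Appendix A, require the Day 0 SMFA for each participant whose post-vaccination SMFA is analysed; otherwise the adjusted analysis loses participants.

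The cost is one degree of freedom and at most one Day 0 assay per analysed participant: up to 60 in the pilot (4 arms × 15), fewer if some are already run. The serum is already scheduled to be drawn. The outcome-based choice of main-phase samples in 17.2.2 needs a separate remedy.

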### 12.6.4 Direct Skin Feeds

While the SMFA is standardized and reproducible and has been shown to correlate with ELISA antibody titers in several species, the parasite strain, gametocyte load in the feeder, and lab colony mosquitoes are all significantly different from those found under field conditions. We believe DSFs, in which insectary-raised clean mosquitoes are directly fed on infected individuals, may be more likely to be predictive of an intervention's impact on transmission than membrane feeds. Thousands of subjects in Bancoumana or neighboring areas have previously been enrolled in direct-feeding tests without significant adverse effects reported. In 1994 and 1995, Toure and colleagues conducted direct feeds on 72 children 2 years of age or more without any risks identified. From 1996 to 1998, Diallo and colleagues conducted DSFs on 372 children 4 to 18 years of age without any safety problems. In 2002 and 2003, DSFs were

carried out in Bancoumana and in a neighboring village on a total of 44 gametocyte carriers 6 to 18 years of age, also without any reported safety problems.

More recently, as described in detail in **Section 4**, the study team in Mali has performed over 10,000 DSFs on subjects older than 5 years since June 2011. All DSF participants were actively followed 24 hours post feed and for as many as 24 DSFs. Except for 1 case of definitely related Grade 2 erythema that resolved within 48 hours and 5 episodes of definitely related Grade 1 pruritus, there have been no other expected or unexpected AEs recorded as definitely, probably, or possibly related to the feeding procedures in either study.

Additionally, under protocol #11-I-N143, multiple DSFs during a 24-hour period have been completed in 18 subjects to date. In these 18 subjects, DSFs were well-tolerated, and there have been no reported AEs resulting from having multiple direct skin feeds completed in a short period of time.

For DSFs, 2 feeding pints with approximately 30 pre-starved female mosquitoes in each will be prepared. Each subject will be exposed to the feeding pints for 15-20 minutes. All subjects will be offered a topical antihistamine and/or topical antipruritic to use following the feeds. Systemic medications may also be prescribed for treatment of local or systemic symptoms following DSFs if clinically indicated.

The total number of mosquitoes used for each DSF will be maintained at appropriately 60 mosquitoes, and no subject will undergo more than 8 DSFs during the study period in Year 1 and no more than 10 DSFs during the study period in Year 2. Note, if subjects 9-18 years of age are not willing to undergo a feed at the time of the DSF, they will not be withdrawn, but rather will be followed per protocol with periodic DSF or without undergoing further DSFs.

In our previous TBV protocols, DSFs started either 1 or 2 weeks post vaccination in order to time the DSFs with expected peak antibody responses. As antibody responses have significantly improved, in peak levels and more importantly durability, the question of functional activity no longer is focused on peak time periods, but rather duration of activity. Thus, at this time it is planned that post Vaccination #3, DSFs will start 14 days post Vaccination #3 and continue every 14 days for 8 total DSF assays. Post Vaccination #4, DSFs will also start 14 days post Vaccination #4 and continue every 14 days for 10 total DSF assays.

Some experiments have already been completed under protocols #13-I-N109 and #11-I-N143 to try to help determine which time of day and body part will maximize positive DSFs. Although there was not a significant difference found between location and time of feed in this small experiment, we did find that feeding at dawn and on the arm were estimated to have the highest counts.

After the feed, surviving mosquitoes will be assessed for infectiousness by microscopy or molecular assays.

#### **12.6.4.1 Withdrawal from DSF**

The following criteria will be checked prior to each DSF and are contraindications to DSFs:

- Severe local or systemic reaction to mosquito bites following a previous DSF.
- Positive urine or serum  $\beta$ -hCG test (pregnancy testing results obtained within the last 7-10 days before the DSF are acceptable; see [Appendix A](#)).
- Acute illness with an oral temperature  $>37.5^{\circ}\text{C}$  at the time of the DSF.
- Any other condition that in the opinion of the Investigator poses a threat to the individual if he/she undergoes DSF or that may complicate interpretation of the safety of DSF.

Recent use of antimalarial medications is not a contraindication to participating in the DSFs. The medication used and time period the medication was taken should be recorded on the subject's source documents and case report forms (CRFs) accordingly.

#### **12.6.5 Entomological Procedures and Insectary Used in DSF**

##### **12.6.5.1 Mosquito Rearing at the Insectary**

A laboratory colony of *A. gambiae (coluzzi)* established from a local catch in 2008 will be used for the DSFs. This colony has been used in the current assay development study and was demonstrated to have similar susceptibility as the F1 progeny of the wild-caught mosquitoes. The colony has been maintained using blood meals collected under standard procedures of the blood transfusion center from local healthy donors. To ensure that the donor is free of potentially transovarial arbovirus in incubation, the donated blood is only used 5-7 days after the collection and after the donor is confirmed to remain healthy during this period. Potentially transovarial arbovirus in mosquitoes or in blood meals may be detected by ELISA and PCR methods. However, it is not feasible to conduct these tests routinely on blood donor volunteers due to highly restricted access to positive controls required in these tests, but blood samples from donors and mosquitoes from the colony are tested for Rift Valley fever (RVF) virus on a regular basis in the US.

The insectary in which mosquitoes are reared in Bamako has been in use for more than 15 years. Security is ensured by the use of double doors, which prevents the escape of reared mosquitoes as well as the entry of non-insectary mosquitoes. Mosquitoes are transported to Bancoumana or Doneguebougou in net-sealed feeding cups secured in wooden holders inside a cooler, with wet towels to maintain adequate humidity. After arrival at the assigned insectary in Bancoumana or Doneguebougou, mosquitoes are secured within the transporting containment. The insectary is adequately equipped with rooms with humidifiers which are regularly monitored according to standard insectary procedures, and access to the insectary is limited to study personnel only.

After feeds, mosquitoes, still in net-sealed cups, are transported back to the insectary in Bamako. All subsequent handling of mosquitoes will take place in Bamako.

